10.5. Appendix 5: Genetics

Use/Analysis of DNA

- Genetic variation may impact a participant's response to study intervention, susceptibility to, and severity and progression of disease. Therefore, where local regulations and IRBs/ECs allow, a blood sample will be collected for DNA analysis.
- The scope of the genetic research may be narrow (eg, 1 or more candidate genes) or broad (eg, the entire genome), as appropriate to the scientific question under investigation.
- The samples may be analyzed as part of a multistudy assessment of genetic factors involved in the response to PF-07260437 or study interventions of this class to understand treatments for the disease(s) under study or the disease(s) themselves.
- The results of genetic analyses may be reported in the CSR or in a separate study summary or may be used for internal decision making without being included in a study report.
- The sponsor will store the DNA samples in a secure storage space with adequate measures to protect confidentiality.
- The samples will be retained as indicated:
 - Retained samples for banking will be stored indefinitely or for another period as per local requirements.
 - Participants may withdraw their consent for the storage and/or use of their Retained Samples at any time by making a request to the investigator; in this case, any remaining material will be destroyed. Data already generated from the samples will be retained to protect the integrity of existing analyses.
 - Samples for genetic research will be labeled with a code. The key between the code and the participant's personally identifying information (eg, name, address) will be held securely at the study site.

10.6. Appendix 6: Liver Safety: Suggested Actions and Follow-Up Assessments

Potential Cases of Drug-Induced Liver Injury

Humans exposed to a drug who show no sign of liver injury (as determined by elevations in transaminases) are termed “tolerators,” while those who show transient liver injury but adapt are termed “adaptors.” In some participants, transaminase elevations are a harbinger of a more serious potential outcome. These participants fail to adapt and therefore are “susceptible” to progressive and serious liver injury, commonly referred to as DILI. Participants who experience a transaminase elevation above $3 \times$ ULN should be monitored more frequently to determine if they are “adaptors” or are “susceptible.”

In the majority of DILI cases, elevations in AST and/or ALT precede TBili elevations ($>2 \times$ ULN) by several days or weeks. The increase in TBili typically occurs while AST/ALT is/are still elevated above $3 \times$ ULN (ie, AST/ALT and TBili values will be elevated within the same laboratory sample). In rare instances, by the time TBili elevations are detected, AST/ALT values might have decreased. This occurrence is still regarded as a potential DILI. Therefore, abnormal elevations in either AST OR ALT in addition to TBili that meet the criteria outlined below are considered potential DILI (assessed per Hy’s law criteria) cases and should always be considered important medical events, even before all other possible causes of liver injury have been excluded.

The threshold of laboratory abnormalities for a potential DILI case depends on the participant’s individual baseline values and underlying conditions. Participants who present with the following laboratory abnormalities should be evaluated further as potential DILI (Hy’s law) cases to definitively determine the etiology of the abnormal laboratory values:

- Participants with AST/ALT and TBili baseline values within the normal range who subsequently present with AST OR ALT values $>3 \times$ ULN AND a TBili value $>2 \times$ ULN with no evidence of hemolysis and an alkaline phosphatase value $<2 \times$ ULN or not available.

For participants with baseline AST OR ALT OR TBili values above the ULN, the following threshold values are used in the definition mentioned above, as needed, depending on which values are above the ULN at baseline:

- Preexisting AST or ALT baseline values above the normal range: AST or ALT values >2 times the baseline values AND $>3 \times$ ULN; or $>8 \times$ ULN (whichever is smaller).
- Preexisting values of TBili above the normal range: TBili level increased from baseline value by an amount of at least $1 \times$ ULN or if the value reaches $>3 \times$ ULN (whichever is smaller).

Rises in AST/ALT and TBili separated by more than a few weeks should be assessed individually based on clinical judgment; any case where uncertainty remains as to whether it represents a potential Hy’s law case should be reviewed with the sponsor.

The participant should return to the investigator site and be evaluated as soon as possible, preferably within 48 hours from awareness of the abnormal results. This evaluation should include laboratory tests, detailed history, and physical assessment.

In addition to repeating measurements of AST and ALT and TBili for suspected Hy's law cases, additional laboratory tests should include albumin, CK, direct and indirect bilirubin, GGT, PT/INR, total bile acids, and alkaline phosphatase. Consideration should also be given to drawing a separate tube of clotted blood and an anticoagulated tube of blood for further testing, as needed, for further contemporaneous analyses at the time of the recognized initial abnormalities to determine etiology. A detailed history, including relevant information, such as review of ethanol, acetaminophen/paracetamol (either by itself or as a coformulated product in prescription or over-the-counter medications), recreational drug, or supplement (herbal) use and consumption, family history, sexual history, travel history, history of contact with a jaundiced person, surgery, blood transfusion, history of liver or allergic disease, and potential occupational exposure to chemicals, should be collected. Further testing for acute hepatitis A, B, C, D, and E infection, liver imaging (eg, biliary tract), and collection of serum samples for acetaminophen/paracetamol drug and/or protein adduct levels may be warranted.

All cases demonstrated on repeat testing as meeting the laboratory criteria of AST/ALT and TBili elevation defined above should be considered potential DILI (Hy's law) cases if no other reason for the LFT abnormalities has yet been found. **Such potential DILI (Hy's law) cases are to be reported as SAEs, irrespective of availability of all the results of the investigations performed to determine etiology of the LFT abnormalities.**

A potential DILI (Hy's law) case becomes a confirmed case only after all results of reasonable investigations have been received and have excluded an alternative etiology.

10.7. Appendix 7: ECG Findings of Potential Clinical Concern

ECG Findings That May Qualify as AE

Marked sinus bradycardia (rate <40 bpm) lasting minutes.New PR interval prolongation >280 ms.New prolongation of QTcF to >480 ms (absolute) or by \geq60 ms from baseline.New-onset atrial flutter or fibrillation, with controlled ventricular response rate: ie, rate <120 bpm.New-onset type I second-degree (Wenckebach) AV block of >30 seconds' duration.Frequent PVCs, triplets, or short intervals (<30 seconds) of consecutive ventricular complexes.
ECG Findings That May Qualify as Serious AE

QTcF prolongation >500 ms.New ST-T changes suggestive of myocardial ischemia.New-onset left bundle branch block (QRS >120 ms).New-onset right bundle branch block (QRS >120 ms).Symptomatic bradycardia.Asystole:
In awake, symptom-free participants in sinus rhythm, with documented periods of asystole \geq3.0 seconds or any escape rate <40 bpm, or with an escape rhythm that is below the AV node.In awake, symptom-free participants with atrial fibrillation and bradycardia with 1 or more pauses of at least 5 seconds or longer.Atrial flutter or fibrillation, with rapid ventricular response rate: rapid = rate >120 bpm.Sustained supraventricular tachycardia (rate >120 bpm) ("sustained" = short duration with relevant symptoms or lasting >1 minute).Ventricular rhythms >30 seconds' duration, including idioventricular rhythm (heart rate <40 bpm), accelerated idioventricular rhythm (HR >40 bpm to <100 bpm), and

monomorphic/polymorphic ventricular tachycardia (HR >100 bpm (such as torsades de pointes)).

- Type II second-degree (Mobitz II) AV block.
- Complete (third-degree) heart block.

ECG Findings That Qualify as SAE

- Change in pattern suggestive of new myocardial infarction.
- Sustained ventricular tachyarrhythmias (>30 seconds' duration).
- Second- or third-degree AV block requiring pacemaker placement.
- Asystolic pauses requiring pacemaker placement.
- Atrial flutter or fibrillation with rapid ventricular response requiring cardioversion.
- Ventricular fibrillation/flutter.
- At the discretion of the investigator, any arrhythmia classified as an adverse experience.

The enumerated list of major events of potential clinical concern are recommended as "alerts" or notifications from the core ECG laboratory to the investigator and Pfizer study team, and not to be considered as all inclusive of what to be reported as AEs/SAEs.

10.8. Appendix 8: Alternative Measures During Public Emergencies

The alternative study measures described in this section are to be followed during public emergencies, including the COVID-19 pandemic. This appendix applies for the duration of the COVID-19 pandemic globally and will become effective for other public emergencies only upon written notification from Pfizer.

Use of these alternative study measures are expected to cease upon the return of business as usual circumstances (including the lifting of any quarantines and travel bans/advisories).

10.8.1. Eligibility

While SARS-CoV2 testing is not mandated for this study, local clinical practice standards for testing should be followed. A patient should be excluded if he/she has a positive test result for SARS-CoV2 infection, is known to have asymptomatic infection, or is suspected of having SARS-CoV2. Patients with active infections are excluded from study participation as per exclusion criterion # 17: Participants with active, uncontrolled bacterial, fungal, or viral infection, including (but not limited to) HBV, HCV, COVID-19/SARS-CoV2, and known HIV or AIDS-related illness. When the infection resolves, the patient may be considered for re-screening.

10.8.2. Telehealth Visits

Study participants who can attend scheduled study visits on site and complete all study procedures as described in the protocol per the [SOA](#) should do so; all other participants should make every effort to participate in study visits by telephone via a telehealth visit. Video contact can be used if available and permitted by local regulations.

In the event that in-clinic study visits cannot be conducted, every effort should be made to follow up on the safety of study participants at scheduled visits per the Schedule of Activities or unscheduled visits. Telehealth visits may be used to continue to assess participant safety and collect data points. Telehealth includes the exchange of healthcare information and services via telecommunication technologies (e.g., audio, video, video-conferencing software) remotely, allowing the participant and the investigator to communicate on aspects of clinical care, including medical advice, reminders, education, and safety monitoring. The following assessments must be performed during a telehealth visit:

- Review and record any AEs and SAEs since the last contact. Refer to [SOA](#) and [Section 8.3](#).
- Review and record any new concomitant medications or changes in concomitant medications since the last contact.
- Review and record contraceptive method and results of pregnancy testing. Confirm that the participant is adhering to the contraception method(s) required in the protocol. Refer to [Appendix 4](#) and [Section 10.8.3.1](#) of this appendix regarding pregnancy tests.

Study participants must be reminded to promptly notify site staff about any change in their health status.

10.8.3. Alternative Facilities for Safety Assessments

If the study participant is unable to visit the study site, protocol specified safety laboratory tests and/or tumor assessments may alternatively be performed at an alternative local laboratory or facility, where allowable by law or local guidance.

10.8.3.1. Laboratory Testing

If a study participant is unable to visit the site for protocol-specified safety laboratory evaluations, testing may be conducted at a local laboratory if permitted by local regulations. The local laboratory may be a standalone institution or within a hospital. All protocol-specified safety laboratory evaluations may be performed at a local laboratory.

If a local laboratory is used, qualified study site personnel must order, receive, and review results. Site staff must collect the local laboratory reference ranges and certifications/ accreditations for filing at the site. Laboratory test results are to be provided to the site staff as soon as possible. The local laboratory reports should be filed in the participant's source documents/medical records. Relevant data from the local laboratory report should be recorded on the CRF.

If a participant requiring pregnancy testing cannot visit a local laboratory for pregnancy testing, a home urine pregnancy testing kit with a sensitivity of at least 25 mIU/mL may be used by the participant to perform the test at home, if compliant with local regulatory requirements. The pregnancy test outcome should be documented in the participant's source documents/medical records and relevant data recorded on the CRF. Confirm that the participant is adhering to the contraception method(s) required in the protocol.

Any results that are considered clinically significant must be reported in a timely manner and as directed in the protocol.

10.8.3.2. Imaging

If the participant is unable to visit the study site for planned or unplanned imaging assessments, the participant may visit an alternative facility to have these assessments performed. Qualified study site personnel must order, receive, and review results.

10.8.3.3. Electrocardiograms

If the participant is unable to visit the study site for ECGs, the participant may visit an alternative facility to have the ECGs performed. Qualified study site personnel must order, receive, and review results.

10.8.4. Study Intervention

If the safety of a trial participant is at risk because they cannot complete required evaluations or adhere to critical mitigation steps, then discontinuing that participant from study intervention must be considered.

The following is recommended for the administration of PF-07260437 for participants who have active COVID-19 confirmed (positive by regulatory authority-approved test) or presumed (test pending/clinical suspicion) SARS-CoV2 infection:

- For symptomatic participants with active SARS-CoV2 infection, PF-07260437 should be delayed for at least 14 days from the start of symptoms. This delay is intended to allow the resolution of symptoms of SARS-CoV2 infection.
- Prior to restarting treatment, the participant should be afebrile for 72 hours, and SARS-CoV2-related symptoms should have recovered to \leq Grade 1 for a minimum of 72 hours. Notify the study team when treatment is restarted.
- Continue to consider potential drug-drug interactions as described in [Section 6.8](#) for any concomitant medication administered for treatment of SARS-CoV2 infection

10.8.5. Home Health Visits

A home health care service may be utilized to facilitate scheduled visits per the Schedule of Activities. Home health visits include a healthcare provider conducting an in-person study visit at the participant's location, rather than an in-person study visit at the site. The following may be performed during a home health visit:

- Review and record any AEs and SAEs since the last contact. Refer to [Section 8.3](#).
- Review and record any new concomitant medications or changes in concomitant medications since the last contact.
- Review and record contraceptive method and results of pregnancy testing. Confirm that the participant is adhering to the contraception method(s) required in the protocol. Refer to [Appendix 4](#).

10.8.6. Adverse Events and Serious Adverse Events

If a participant has COVID-19 during the study, this should be reported as an AE or SAE and appropriate medical intervention provided. Study intervention should continue unless the investigator/treating physician is concerned about the safety of the participant, in which case temporary or permanent discontinuation may be required.

It is recommended that the investigator discuss temporary or permanent discontinuation of study intervention with the study medical monitor.

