6.5.1. Dosing Interruptions

With respect to study intervention, participants experiencing Grade 3 or 4 potentially treatment-related toxicity or intolerable Grade 2 toxicity despite supportive treatment should have their treatment interrupted as indicated in [Table 10](#) and [Table 11](#).

Appropriate follow-up assessments should be done until adequate recovery occurs as assessed by the investigator. Criteria required before treatment can resume are described in [Section 6.5.2](#).

Doses may be held up to 4 weeks until toxicity resolution. Depending on when the AE resolved, a treatment interruption may lead to the participant missing subsequent planned doses within that same cycle or to delay the initiation of the subsequent cycle as follows:

- If the planned Day 1 dose (of any cycle) cannot be administered due to an AE, then Day 1 dose will be delayed until the AE has resolved and the study drug can be administered.
- If the planned Day 15 dose (of any cycle) is delayed for ≤ 7 days, then the planned day 15 dose can be administered as the delayed Day 15 dose. Day 1 of the subsequent cycle will be administered 2 weeks after the delayed Day 15 dose.
- If the planned Day 15 dose (of any cycle) is delayed for >7 days, then Day 15 will be skipped. The next dose will be administered when the AE has resolved and will be considered the Day 1 dose of the subsequent cycle.

The need for a dose reduction at the time of treatment resumption should be based on the criteria defined in the [Dose Reductions section](#), unless expressly agreed otherwise following discussion between the investigator and the sponsor.

In the event of a treatment interruption for reasons other than treatment-related toxicity (eg, elective surgery) lasting >4 weeks, treatment resumption will be decided in consultation with the sponsor.

See [Appendix 8, Section 10.8.4](#) for COVID-19 related dose interruption.

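### For symptomatic COVID-19 with no physician concern, Protocol 10.8.6 sets the opposite dosing default to 10.8.4 and does not refer to it

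*Protocol*

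**What the plan says.** Two subsections of Protocol Appendix 8 deal with dosing in a participant who has COVID-19.

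- **Section 10.8.6** (adverse events) has COVID-19 on study reported as an AE or SAE, then says: "Study intervention should continue unless the investigator/treating physician is concerned about the safety of the participant". If there is concern, temporary or permanent discontinuation may be needed. It adds: "It is recommended that the investigator discuss temporary or permanent discontinuation of study intervention with the study medical monitor". It does not separate symptomatic from asymptomatic infection and does not mention 10.8.4.
- **Section 10.8.4** (study intervention) covers confirmed or presumed active infection and opens as advice: "The following is recommended for the administration of PF-07260437". It continues: "For symptomatic participants with active SARS-CoV2 infection, PF-07260437 should be delayed for at least 14 days from the start of symptoms". On restart it says: "Prior to restarting treatment, the participant should be afebrile for 72 hours", with symptoms at Grade 1 or lower for at least 72 hours as well. The hold does not depend on physician concern.

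Section 6.5.1 sends the reader to 10.8.4 "for COVID-19 related dose interruption". Its own timing rules are introduced by "Doses may be held up to 4 weeks until toxicity resolution" and include "If the planned Day 15 dose (of any cycle) is delayed for >7 days, then Day 15 will be skipped". The introduction to Appendix 8 says its measures are to be followed in public emergencies and does not rank them. SAP Section 5.4 covers COVID-19 data handling, not dosing.

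**The concern.** A site that handles COVID-19 as an adverse event will naturally turn to 10.8.6. There it finds continued dosing as the starting point, and nothing directs it to the 14-day hold two subsections earlier.

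What is at stake is safety first, then interpretation. Section 2.2.4 states that there are no clinical data yet for this agent. Section 6.8.2.1 lists fever and shortness of breath among the common CRS symptoms and warns that CRS can be hard to tell from other conditions. Appendix 11 grades CRS on fever, hypotension and hypoxia only where no other cause explains them. Those grades drive decisions in escalation cohorts of about 3 participants: Grade 3 or higher CRS of any duration is a DLT (Section 4.3.6.2), and Grade 2 or higher CRS lasting over 24 hours in more than one participant despite treatment can trigger priming (Section 4.1). A dose given during a febrile respiratory infection makes that attribution harder.

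The entry rules are also stricter than 10.8.6. Exclusion criterion 17 and Section 10.8.1 keep out patients with a positive test, known asymptomatic infection or suspected infection.

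**Working it through.** No arithmetic applies. The question is whether the two subsections can both be followed, so each possible situation is set against both texts.

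| Situation | 10.8.4 | 10.8.6 | Compatible? |
|---|---|---|---|
| Symptomatic, physician concerned | Hold at least 14 days, then the 72-hour recovery conditions | Temporary or permanent discontinuation may be required; no minimum hold | Yes, though 10.8.6 gives no duration |
| Symptomatic, physician not concerned | Same hold and recovery conditions | Continue | **No: opposite defaults** |
| Asymptomatic | No hold stated | Continue unless concerned | Yes |

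The conflict is confined to the second row.

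Next, does any text settle that row?

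1. Section 6.5.1 names 10.8.4, and not 10.8.6, for COVID-19 dose interruption. This favours 10.8.4.
2. 10.8.4 is the subsection on study intervention and gives specific conditions, while 10.8.6 is about event reporting. This also favours 10.8.4.
3. 10.8.6 carries no exception for symptomatic infection and no reference to 10.8.4.
4. The Appendix 8 introduction gives all its measures equal standing.
5. 10.8.4 presents itself as a recommendation, so it does not override 10.8.6 by its own force.

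Points 1 and 2 show the likely intent. Points 3 to 5 show that a reader has to infer it.

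Last, do the Section 6.5.1 timing rules reach a COVID-19 hold? The lead-in speaks of toxicity, but the bullets on the Day 1 dose and on the skipped Day 15 dose turn on an AE, and 10.8.6 makes COVID-19 an AE. They plausibly apply already, though this is not stated.

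**The case against.** The strongest reply is that the protocol already shows which text governs and that other safeguards exist. Most of this stands. The operative dosing section points to 10.8.4 by number. Section 8 asks for safety issues to be taken to the sponsor at once to decide whether a participant should continue or stop. Section 6.5.2 bars starting a new cycle until nonhematologic toxicity has recovered, although it does not clearly cover a Day 15 dose and COVID-19 may not count as a toxicity. Because 10.8.4 is only a recommendation, departing from it would not clearly be a protocol deviation even if 10.8.6 were silent.

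Three stronger readings are tempting, and the documents do not support them.

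- *That physician concern is the only check on continued dosing.* The medical monitor sentence in 10.8.6 concerns stopping, but the Section 8 request covers continuing as well.
- *That the inconsistency costs a countable number of DLT-evaluable participants.* A delayed or skipped second dose would follow from the 10.8.4 hold itself, so it does not measure the conflict, and the documents give no infection incidence. A skipped dose also does not clearly remove a participant. Section 4.3.6 and SAP Table 1 require all planned dosing, whereas the estimand text (Protocol 9.1.1.1, SAP 2.1.1) excludes those without a DLT who withdraw from treatment before 2 full doses.
- *That this is a flaw in the trial design.* No design element or analysis depends on it.

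What remains after the reply is a safety instruction that has to be reconciled by inference.

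**Conclusion.** The inconsistency is real and narrow. It affects only symptomatic COVID-19 where the physician has no safety concern, and only while Appendix 8 is in force, that is, during the COVID-19 pandemic or another public emergency notified by the sponsor. 10.8.4 is evidently meant to govern, but 10.8.6 can be read on its own as permitting dosing through febrile infection. Its importance lies in participant safety and in clean attribution of CRS and DLTs during Part 1. No size can be put on it from the documents, and none is claimed.

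The conclusion rests on reading 10.8.6 as written, for any participant with COVID-19, and on taking the 6.5.1 pointer as evidence of intent, not as a rule of precedence. It should be treated as a minor internal inconsistency that is worth correcting because the remedy is so small.

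**What to change.** Amend the dosing sentence in 10.8.6 to make two statements. In symptomatic confirmed or presumed SARS-CoV2 infection, PF-07260437 is delayed and restarted as set out in 10.8.4, with dose timing under 6.5.1. In asymptomatic infection, dosing may go on unless the investigator has a safety concern. Keep the sentence about consulting the medical monitor. Naming 6.5.1 also makes explicit that its timing rules apply to COVID-19 holds.

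The cost is one sentence with two cross-references and no change to the design or analysis. The small downside is that some Cycle 1 participants held under 10.8.4 may need replacement. Section 4.3.6 already allows this for participants who are not DLT-evaluable, and SAP 5.4(a) allows it for those who drop out because of COVID-19.
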